3.9.1.1. Other significant AEs

In addition, incidence of a selected subset of relevant AEs in this class of drugs (eg, Extrapyrimal symptom (EPS) TEAEs, AEs associated with abuse potential, AEs associated with drug withdrawal, and suicide related events, etc.) will be summarized by treatment group and preferred term. The selection of AEs per subset will be based on the preferred term, Standardized MedDRA queries (SMQs) or customized MedDRA queries (CMQs).

3.9.2. Clinical Laboratory Parameters

Laboratory parameters will be presented in conventional (ie, US) units. Unless specified otherwise, only scheduled laboratory parameters will be included in the summaries. All laboratory data, including those collected at unscheduled visits, will be included in the listings.

Laboratory results (baseline and change from baseline) for the Safety Population during double-blind treatment period for chemistry and hematology parameters will be summarized by treatment group and by visit.

Number (percentage) of subjects with potentially clinically significant (PCS) values at any post-baseline visit, will be summarized by treatment group. PCS criteria are presented in [Table 1](#). The denominator is all subjects with non-PCS baseline and at least one post-baseline assessment in the Safety Population and the numerator is the number of subjects with non-PCS baseline and PCS at post-baseline. All PCS values including baseline PCS values will be included in supportive listings.

Shift tables for metabolic parameters (fasting glucose, total cholesterol, LDL, HDL, Triglycerides, and HbA1c) and liver function tests will be presented. The criteria are summarized in [Table 2](#), [Table 3](#) and [Table 4](#).

Table 1: Criteria of Potentially Clinically Significant (PCS) Abnormality for Selected Analytes

Parameters	Criteria
Chemistry	
Albumin	<2.5 g/dL
Alkaline Phosphatase (U/L)	$\geq 3 \times \text{ULN}$
Alanine Aminotransferase (U/L)	$\geq 3 \times \text{ULN}$
Aspartate Aminotransferase (U/L)	$\geq 3 \times \text{ULN}$
Bilirubin, Total	$\geq 2.0 \text{ mg/dL}$
Blood Urea Nitrogen	$> 30 \text{ mg/dL}$
Cholesterol, Random	$> 300 \text{ mg/dL}$
Cholesterol, Fasting	$\geq 240 \text{ mg/dL}$
Cholesterol, HDL Fasting	$\leq 30 \text{ mg/dL}$
Cholesterol, LDL Fasting	$\geq 160 \text{ mg/dL}$
Creatine Kinase (U/L)	$\geq 3 \times \text{ULN}$
Creatinine	$\geq 2.0 \text{ mg/dL}$
Glucose, Random	$< 50 \text{ mg/dL}$ or $\geq 200 \text{ mg/dL}$
Glucose, Fasting	$< 50 \text{ mg/dL}$ or $\geq 126 \text{ mg/dL}$
Potassium	$< 3 \text{ mmol/L}$ or $> 5.5 \text{ mmol/L}$
Lactate Dehydrogenase (U/L)	$> 3 \times \text{ULN}$
Prolactin (Female)	$> 30 \text{ ng/mL}$
Prolactin (Male)	$> 20 \text{ ng/mL}$
Sodium	$< 130 \text{ mmol/L}$ or $> 150 \text{ mmol/L}$
Triglycerides, Fasting (Female)	$\geq 120 \text{ mg/dL}$
Triglycerides, Fasting (Male)	$\geq 160 \text{ mg/dL}$

Table 1: Criteria of Potentially Clinically Significant (PCS) Abnormality for Selected Analytes (Continued)

Parameters	Criteria
Hematology	
Eosinophils	$>1.0 \times 10^3/\mu\text{L}$
Hematocrit (Female)	$\leq 32\%$
Hematocrit (Male)	$\leq 37\%$
Neutrophils, Absolute	$<1.5 \times 10^3/\mu\text{L}$
Platelets	$<75.0 \times 10^3 \text{ cells}/\mu\text{L}$ or $\geq 700.0 \times 10^3 \text{ cells}/\mu\text{L}$
Leukocytes	$\leq 2.8 \times 10^3/\mu\text{L}$ or $\geq 16.0 \times 10^3/\mu\text{L}$

Table 2: Shifts Category from Baseline to Any Post-Baseline for Selected Lipid Parameters

Total cholesterol (fasting) mg/dL
Normal (<200) to high (≥ 240)
Borderline (≥ 200 and < 240) to high (≥ 240)
Normal/Borderline (<240) to high (≥ 240)
Normal (<200) to borderline/high (≥ 200)
Increase ≥ 40 mg/dL
LDL Cholesterol (fasting) mg/dL
Normal (<100) to high (≥ 160)
Borderline (≥ 100 and <160) to high (≥ 160)
Normal/borderline (<160) to high (≥ 160)
Normal (<100) to borderline/high (≥ 100)
Increase ≥ 30 mg/dL
HDL Cholesterol (fasting) mg/dL
Normal (≥ 40) to low (<40)
Decrease ≥ 20 mg/dL
Triglycerides (fasting) mg/dL
Normal (<150) to high (≥ 200)
Normal (<150) to very high (≥ 500)
Borderline (≥ 150 and <200) to high (≥ 200)

Table 2: Shifts Category from Baseline to Any Post-Baseline for Selected Lipid Parameters (Continued)

Triglycerides (fasting) mg/dL
Borderline (≥ 150 and < 200) to very high (≥ 500)
Normal/borderline (< 200) to high (≥ 200)
Normal/borderline (< 200) to very high (≥ 500)
Normal (< 150) to borderline/high/very high (≥ 150)
Increase ≥ 50 mg/dL

Table 3: Shift Category from Baseline to Any Post-baseline in Glucose and HbA1c

Serum glucose (fasting) mg/dL
Normal (< 100) to high (≥ 126)
Impaired (≥ 100 and < 126) to high (≥ 126)
Normal/Impaired (< 126) to high (≥ 126)
Increase ≥ 10 mg/dL
HbA1c%
Shift from baseline ($< 5.7\%$) to post-baseline $\geq 5.7\%$
Shift from baseline ($< 5.7\%$) to post-baseline $\geq 5.7\%$ and $< 6.5\%$
Shift from baseline ($< 5.7\%$) to post-baseline $\geq 6.5\%$

Table 4: Shift Category from Baseline to Any Post-Baseline in Liver Function Test

Alanine Aminotransferase (ALT) (U/L)
Shift from Normal to $\geq 3 \times$ ULN
Shift from Normal to $\geq 5 \times$ ULN
Shift from Normal to $\geq 10 \times$ ULN
Aspartate Aminotransferase (AST) (U/L)
Shift from Normal to $\geq 3 \times$ ULN
Shift from Normal to $\geq 5 \times$ ULN
Shift from Normal to $\geq 10 \times$ ULN
Bilirubin, Total (mg/dL)
Shift from Normal to $> 1 \times$ ULN
Shift from Normal to $\geq 2 \times$ ULN

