#### 7.2.5. Criteria Based on Laboratory Assessments

24. Subject has a laboratory abnormality that would compromise the well-being of the subject, or has any of the following specific laboratory results at Visit 1:
  - Aspartate aminotransferase (AST) or alanine aminotransferase (ALT) value  $\geq 2$  times the upper limit of the laboratory normal reference range
  - Absolute neutrophil count (ANC)  $\leq 1.5 \times 10^3 \mu\text{L}$
  - Platelet count  $\leq 75 \times 10^3 \mu\text{L}$
  - Serum creatinine  $> 2.5 \text{ mg/dL}$
  - Positive pregnancy test result
25. Subject has a positive serology test for hepatitis B surface antigen, hepatitis C antibody confirmed by RNA testing, or human immunodeficiency virus (HIV) antibody at Visit 1
26. Subject has dyslipidemia, defined for this study as total fasting cholesterol  $> 280 \text{ mg/dL}$  or fasting triglycerides  $> 500 \text{ mg/dL}$ , at Visit 1
27. Subject has a Hemoglobin A1c (HbA1c)  $\geq 6.0\%$  at Visit 1
28. Subject has a fasting plasma glucose  $\geq 126 \text{ mg/dL}$  (7.0 mmol/L) at Visit 1
29. Subject has a clinically significant ECG abnormality at Visits 1 or 2
  - Subject has a QT interval  $> 450 \text{ msec}$  for men and  $> 470 \text{ msec}$  for women, as corrected by the Fridericia formula (QTcF), observed at Visits 1 or 2

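### The SAP's by-arm tables never count subjects whose fasting triglycerides rise from 200–499 mg/dL at baseline to 500 or more

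*SAP*

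**What the plan says.** SAP section 3.9.2 plans two kinds of by-arm count for fasting triglycerides.

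- **PCS summary (Table 1).** The limit is 120 mg/dL or more for women ("Triglycerides, Fasting (Female)") and 160 or more for men ("Triglycerides, Fasting (Male)"). The rate is restricted by baseline: "The denominator is all subjects with non-PCS baseline and at least one post-baseline assessment in the Safety Population". The numerator carries the same restriction.
- **Shift table (Table 2).** The bands are the same for both sexes: normal below 150, borderline 150 to under 200, high from 200, very high from 500. There are seven category rows, among them "Normal (<150) to high (≥ 200)", "Normal (<150) to very high" and "Borderline (≥ 150 and < 200) to very high (≥ 500)". An eighth row counts any rise of at least 50 mg/dL whatever the baseline.

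The entry limit is exclusion 26 in Protocol section 7.2.5, which begins "Subject has dyslipidemia, defined for this study as total fasting cholesterol". For triglycerides it bars only fasting values above 500 mg/dL at Visit 1.

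Table 4 ("Shift Category from Baseline to Any Post-Baseline in Liver Function Test") counts ALT and AST at 3, 5 and 10 times the upper limit of normal (ULN), each from a normal baseline only.

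**The concern.** A very high tier exists so that a reader can see how many subjects in each arm reached that level. Subjects who enter at 200–499 are the closest to it. If the rows into the tier all start below 200, the count leaves out the baseline group from which a crossing is most likely. The PCS summary cannot make up for this, because the same subjects are already PCS at baseline and are removed from it.

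The protocol's introduction (section 5.1) presents the combination as lowering the risk of weight gain and of the metabolic problems that go with it, and fasting lipids are listed among the other endpoints. A reader of the safety section would reasonably take the Table 2 rows as the arm comparison for very high triglycerides. As laid out, they compare only subjects who started below 200.

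**Working it through.** The plan states no figure to reproduce. The check is one of coverage: take each possible baseline and ask which planned count would record a move to 500 or more.

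**Inputs.** PCS limits 120 (women) and 160 (men): SAP Table 1. Bands 150, 200 and 500, and the rise of 50: SAP Table 2. Entry limit 500 at Visit 1: Protocol 7.2.5.

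**Step 1: the seven category rows.**

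| Baseline required | Post-baseline counted |
|---|---|
| below 150 | 150 or more |
| below 150 | 200 or more |
| below 150 | 500 or more |
| 150 to under 200 | 200 or more |
| 150 to under 200 | 500 or more |
| below 200 | 200 or more |
| below 200 | 500 or more |

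No row admits a baseline of 200 or more. Testing every whole-number pair with baseline 200–499 and post-baseline 500–1000 against these rows gives zero matches.

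**Step 2: the PCS summary.** Every baseline in 200–499 is at or above both 120 and 160. These subjects are PCS at baseline in both sexes, so they are outside the numerator and the denominator.

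**Step 3: the row for a rise of at least 50.** A subject starting at 450 or below needs a rise of at least 500 − 450 = 50 to reach 500, so is always counted here, but only as a rise and not as having reached 500. A subject starting at 451–499 can reach 500 with a smaller rise. The extremes are 451 to 500 (a rise of 49) and 499 to 548 (a rise of 49). Such a subject is in no triglyceride row unless another post-baseline value is at least 50 above baseline.

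**Step 4: how many subjects.** The documents give no triglyceride distribution, so this step rests on assumptions: log-normal values, median 90–130 mg/dL, log-SD 0.45–0.55, 25–40% of the log variance within subject, a 10% mean rise on treatment, and baselines below 500. The eight post-baseline fasting samples (Visits 3, 4, 6, 9, 11, 13, 15 and 17) come from Protocol Table 3. Simulating 400,000 subjects at each grid point gives:

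- subjects with any post-baseline value of 500 or more: about 0.1% to 5%;
- subjects who do so from a baseline of 200–499: 0.08% to 4.0%;
- the second group as a share of the first: 65% to 96%;
- subjects in no row at all (Step 3): under 0.03%.

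Per arm of 200: 0.0008 × 200 ≈ 0.2 to 0.040 × 200 = 8 subjects. Per arm of 270: 0.0008 × 270 ≈ 0.2 to 0.040 × 270 ≈ 11.

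**Step 5: does Table 4 have the same gap?** Exclusion 24 bars ALT or AST at or above 2 × ULN at Visit 1, and PCS starts at 3 × ULN. A subject with baseline between 1 and 2 × ULN is not PCS at baseline. If that subject reaches 5 or 10 × ULN, the PCS summary counts it. What is lost is the grade, not the subject.

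**The case against.** The strongest reply is that nothing disappears from the report. Section 3.9.2 lists all PCS values, including those of subjects PCS at baseline, so every value of 500 or more is listed. Change in fasting triglycerides is analysed by MMRM with baseline as covariate (section 3.8.6), on linear and log scales (section 3.1), and nobody is dropped for a high baseline. Abnormal results that the investigator judges clinically significant become adverse events (Protocol 13.1). Further metabolic analyses sit in an exploratory plan that is not available here. The baseline restriction applies equally to both randomized arms, and no hypothesis test is involved. All of this stands and limits the point. None of it, in the documents at hand, supplies a by-arm count of subjects reaching 500.

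Three stronger readings are tempting, and the documents do not support them.

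- **That the PCS limits are wrong because they overlap the shift bands.** A woman at 120–149 is PCS and normal, and a man at 160–199 is PCS and borderline. But a PCS flag and a shift category are separate displays, and nothing requires them to match; HDL also differs (PCS at 30 or below, low below 40). Total cholesterol (240), LDL (160) and fasting glucose (126) do match, so it is fair to ask for a reason. Moving the PCS limit to 200 would only duplicate the existing row from below 200 to 200 or more.
- **That the PCS rate mostly records crossings within the normal or borderline bands.** On the assumed grid, the share of newly PCS men whose highest value stays below 200 is 31–61%, so this fails over much of the range. For women it is 56–90%, but only 21–51% stay within normal.
- **That Table 4 has the same gap.** Step 5 shows that it does not.

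**Conclusion.** The gap is real and narrow. From the tables as written, with no distributional assumption, a move from 200–499 to 500 or more is never tabulated by arm as reaching 500. Most of these subjects show up only as a rise of at least 50, and a very few may show up nowhere in the triglyceride rows.

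The size is small and uncertain: about 0.1% to 4% of subjects, and it rests wholly on the assumed median, spread, within-subject variance and mean rise. The 65–96% share is a share of that small group and should not be read alone.

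A reader might infer that the metabolic comparison between arms is compromised. It is not. The effect is confined to the descriptive count of very high triglycerides, which omits the subjects closest to the threshold. The primary, key secondary and model-based lipid analyses are untouched.

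**What to change.** - **Needed:** add a triglyceride row to SAP Table 2 for baseline 200 to under 500 moving to 500 or more. A single row from any baseline below 500 to 500 or more would also do, and gives the full by-arm count in one line.
- **Clarify:** keep the sex-specific PCS limits in Table 1, and add a sentence saying why they do not coincide with the shift-table cut-off for high, when those for total cholesterol, LDL and fasting glucose do. Keeping them also preserves comparability with any earlier reports that used the same limits.
- **Optional:** in Table 4, also count ALT and AST at 5 × ULN or more and 10 × ULN or more from any lower baseline, so that the degree of elevation is shown for subjects who enter above normal.

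The cost is one or a few extra rows in the SAP and the table shells. No visit, sample or collected variable changes.

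### The SAP's liver shift table grades ALT and AST rises only from a normal baseline, so admitted subjects with raised values are not counted by arm at 5× or 10×ULN

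*SAP*

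**What the plan says.** SAP 3.9.2 commits to shift tables for the liver: "Shift tables for metabolic parameters (fasting glucose, total cholesterol, LDL, HDL, Triglycerides, and HbA1c) and liver function tests will be presented". The criteria are in SAP Table 4. For ALT and for AST it has three rows each, at 3×, 5× and 10×ULN, and all six begin "Shift from Normal to", for example "Shift from Normal to $\geq 5 \times$ ULN" and "Shift from Normal to $\geq 10 \times$ ULN". There is no row for a raised baseline or for any baseline, and no denominator is given for the shift tables.

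Protocol 7.2.5, exclusion 24, sets the entry limit on "Aspartate aminotransferase (AST) or alanine aminotransferase (ALT) value" at 2 or more "times the upper limit of the laboratory normal reference range", judged at Visit 1. Values above ULN but below 2×ULN are therefore eligible.

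SAP Table 1 has one PCS threshold for ALT and for AST, 3×ULN or more. Its population is wider than that of Table 4: "The denominator is all subjects with non-PCS baseline and at least one post-baseline assessment in the Safety Population". A baseline between 1× and 2×ULN is non-PCS, so these subjects are in the Table 1 denominator. PCS values are also listed by subject.

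**The concern.** Safety and tolerability is the study's secondary objective, and Table 4 is the only table in the SAP text that separates moderate from large aminotransferase rises by arm. It leaves out a group that the protocol admits by design and that starts closest to the thresholds. For these subjects a rise to 3×ULN and a rise to 10×ULN give the same single count in Table 1. A reader who takes Table 4 as the trial's tally of 5× and 10×ULN cases would be reading a tally for normal-baseline subjects only.

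The SAP uses a wider form elsewhere. Tables 2 and 3 have rows that start from a borderline, impaired or combined normal/borderline baseline for total cholesterol, LDL, triglycerides and fasting glucose. Protocol 14.6 promises laboratory shifts by arm without restricting them to subjects who start normal.

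**Working it through.** The plan states no figure on this point, so there is nothing to reproduce. The check is a classification of hypothetical subjects under the written rules.

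**Inputs**
- Entry limit: excluded at ALT or AST ≥2×ULN at Visit 1 (Protocol 7.2.5).
- Table 1 rule: counted if baseline <3×ULN and a post-baseline value is ≥3×ULN (SAP 3.9.2).
- Table 4 rule: graded at 3×, 5× or 10×ULN if baseline is normal and a post-baseline value reaches that level (SAP 3.9.2).
- Assumption: normal means at or below 1×ULN, since Table 4 gives no cut-off.

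**Classification** (baseline and highest scheduled post-baseline value, both in multiples of ULN)

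| Baseline | Peak | Table 1 | Table 4 rows entered |
|---|---|---|---|
| 0.8 or 1.0 | 2.9 | not counted | none |
| 0.8 or 1.0 | 3 | counted | 3× |
| 0.8 or 1.0 | 5 | counted | 3×, 5× |
| 0.8 or 1.0 | 10 | counted | 3×, 5×, 10× |
| 1.2, 1.5, 1.9 or 1.99 | 2.9 | not counted | none |
| 1.2, 1.5, 1.9 or 1.99 | 3 | counted | none |
| 1.2, 1.5, 1.9 or 1.99 | 5 | counted | none |
| 1.2, 1.5, 1.9 or 1.99 | 10 | counted | none |

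For normal baselines the tables work as intended. For admitted raised baselines, every rise to 3×ULN or more is detected in Table 1 and none is graded above that level.

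**How many subjects could be concerned.** The documents do not say how many subjects start above ULN. If the share were between 5% and 20% (an assumption made only to show scale):
- initial target: 0.05 × 400 = 20 to 0.20 × 400 = 80 subjects;
- increased target: 0.05 × 540 = 27 to 0.20 × 540 = 108 subjects.

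These are subjects who could not enter an ALT or AST row of Table 4. They are not cases of liver injury. The number of 5× or 10×ULN cases among them cannot be derived from the documents.

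**One further detail.** The entry limit applies at Visit 1, but SAP 3.1 takes baseline as the last value before the first dose, and Protocol Table 3 schedules chemistry again at Visit 2. An analysis baseline could therefore reach 2×ULN or more, so the group may be slightly wider than the entry limit suggests.

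**After the fix.** A subject going from 1.5× to 10×ULN would enter all three new rows, and one going from 1.5× to 3×ULN would enter only the first.

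**The case against.** The strongest reply is that nothing is hidden. Table 1 counts these subjects by arm at 3×ULN and the listings show each value. Subtracting the 3× count in Table 4 from the Table 1 count gives, by arm, the raised-baseline subjects who reached 3×ULN, and those few can be graded by hand from the listing. By-visit chemistry summaries cover the whole Safety Population and include the maximum. Values that the investigator judges clinically significant become adverse events, which are tabulated by severity. Normal-only rows are also a legitimate choice, because they keep pre-existing elevation out of a count of new elevation. Table 3 does the same for HbA1c, starting only from below 5.7% although entry admits values below 6.0%. Finally, the table shells are in a separate document that is not available here.

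Much of this stands. Detection at 3×ULN at scheduled visits is covered, and the grading is recoverable. But none of these sources gives a count with a denominator by arm at 5× and 10×ULN:
- A maximum shows that one extreme value occurred, not how many subjects had one.
- Adverse event severity is graded by interference with usual activities (Protocol 13.4), not by multiples of ULN.
- Listings are not a summary, and the SAP is not consistent on them. Section 3.9.2 lists unscheduled laboratory data, while Section 7 leaves unscheduled measurements out of subject listings.

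The point about table shells also stands, so the statement is limited to tables specified in the SAP text.

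Some stronger readings are tempting but unsupported:
- **The subjects are lost.** They are not; they are counted once in Table 1.
- **The table favours one arm.** The baseline condition is stated openly and applies equally to both randomized arms. Nothing in the documents shows a difference between arms in who is left out.
- **One or two omitted cases would change the comparison, or some share of severe cases is missed.** Either claim needs the raised-baseline share and the event rates, which the documents do not give. Protocol 5.2.1 reports no trends or clinically meaningful laboratory changes in the samidorphan studies.
- **Bilirubin has the same gap.** In its first row (above 1×ULN), a baseline below the row's threshold is essentially the normal baseline already used. For its second row (2×ULN), Table 1 has a PCS criterion of 2.0 mg/dL from any non-PCS baseline. If the ULN is at least 1.0 mg/dL (an assumption), that criterion already counts every such subject who reaches 2×ULN.
- **The borderline rows in Tables 2 and 3 prove a mistake.** The HbA1c rows show that the SAP varies by analyte. That makes wider liver rows consistent with its practice, not obligatory.

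**Conclusion.** The point holds as a small gap in the presentation of safety data, for ALT and AST only. Subjects with a baseline above ULN and below 2×ULN are admitted and are counted once if they reach 3×ULN. No table specified in the SAP text counts them by arm at 5× or 10×ULN. What is missing is severity grading, not detection.

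The size is unknown. The 20 to 80 of 400 (27 to 108 of 540) rests wholly on an assumed 5% to 20% share with a raised baseline, and it counts subjects outside the table, not events. The conclusion also assumes that normal in Table 4 means at or below ULN.

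This is a cheap improvement rather than an error. It does not touch the primary or key secondary analyses.

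**What to change.** In SAP Table 4, for ALT and for AST, add three rows each:
- baseline <3×ULN to ≥3×ULN
- baseline <5×ULN to ≥5×ULN
- baseline <10×ULN to ≥10×ULN

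State the denominator for each row: Safety Population subjects below that row's threshold at baseline who have at least one post-baseline value. Keep the existing normal-baseline rows as a labelled subset, so that new elevation from a normal start can still be read separately.

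The cost is six more table rows and a sentence on the denominator. No new data are needed. Counts in the new rows may be slightly higher than in the normal-baseline rows and cannot be lower, because they cover a wider group.

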3.9.3. Vital signs, and Electrocardiograms

3.9.3.1. Vital Signs

Descriptive statistics for vital signs and changes from baseline values at each scheduled time point will be presented by treatment group for the double-blind period.

Vital sign values will be considered PCS if they meet both the observed-value criteria and the change from-baseline criteria listed in Table 5. The number and percentage of subjects with PCS post-baseline values will be tabulated by treatment group for the double-blind treatment period. The percentages will be calculated relative to the number of subjects with available non-PCS baseline values and at least 1 post-baseline assessment for the double-blind period. The numerator will be the total number of subjects with available baseline values and at least 1 PCS post-baseline value for double-blind period. A supportive tabular display of subjects with PCS post-baseline values will be provided, including the subject ID number, and baseline and all post-baseline (including non-PCS) values.

All vital signs will be presented in the subject data listing.

Orthostatic hypotension (20/10) is defined as a fall in systolic blood pressure of at least 20 mmHg and a fall in the diastolic blood pressure of at least 10 mmHg upon standing from supine. Orthostatic hypotension (30) is defined as a fall in systolic blood pressure of at least 30 mmHg upon standing from supine.

Orthostatic tachycardia is defined as a heart rate increase of 30 beats per minute (bpm) or more upon standing from supine, or over 120 bpm upon standing.

The number and percentage of subjects with orthostatic hypotension or orthostatic tachycardia occurring at any post-baseline visit will also be summarized by treatment group for the double-blind period.

Table 5: Criteria for Potentially Clinically Significant (PCS) Blood Pressure or Pulse Rate

Parameter	Criteria
Supine Systolic Blood Pressure	≤ 90 and decrease ≥ 20 mm Hg ≥ 180 and increase ≥ 20 mm Hg
Supine Diastolic Blood Pressure	≤ 50 and decrease ≥ 15 mm Hg ≥ 105 and increase ≥ 15 mm Hg
Supine Heart Rate	≤ 50 and decrease ≥ 15 bpm ≥ 120 and increase ≥ 15 bpm

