### 5.2.2. Olanzapine

Olanzapine has been available in the US since 1996 (Zyprexa®) and was originally approved for the treatment of schizophrenia, but has since been approved for other indications including the treatment of schizophrenia in adolescents and bipolar disorder. The safety and tolerability profile of olanzapine is well documented, and adverse event labeling is supported by an extensive safety database that includes over 8,500 adult patients ([Eli Lilly and Company 2016](#)). Commonly reported AEs consistent across all or most dosage forms in short-term, placebo controlled trials include somnolence, constipation, dry mouth, accidental injury, weight gain, postural hypotension, dizziness, asthenia, fever, and abnormal gait.

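### The two orthostatic hypotension rules leave isolated systolic falls of 20–29 mmHg and isolated diastolic falls out of every measured-incidence table; add component rows.

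*SAP*

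**What the plan says.** SAP 3.9.3.1 (Vital Signs) has two categories. The (20/10) category requires "a fall in systolic blood pressure of at least 20 mmHg and a fall in the diastolic blood pressure of at least 10 mmHg" on standing from supine. The other has no diastolic condition: "Orthostatic hypotension (30) is defined as a fall in systolic blood pressure of at least 30 mmHg upon standing from supine". The tabulated result, by treatment group, is "The number and percentage of subjects with orthostatic hypotension or orthostatic tachycardia occurring at any post-baseline visit".

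The neighbouring tachycardia rule joins its two limbs with *or*: "a heart rate increase of 30 beats per minute (bpm) or more upon standing from supine, or over 120 bpm upon standing".

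The same section has PCS criteria, under which vital signs count if "they meet both the observed-value criteria and the change from-baseline criteria listed in Table 5". Every row of Table 5 is a supine measure compared with baseline, for example "Supine Diastolic Blood Pressure". None concerns the change from supine to standing. The section also provides descriptive statistics by visit, and "All vital signs will be presented in the subject data listing".

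Protocol Table 3 (vital signs footnote) and Protocol 8.3.5 require blood pressure after 5 minutes supine and again after 2 minutes standing. The protocol does not define orthostatic hypotension. Protocol 5.2.2 names it among the commonly reported olanzapine events: "weight gain, postural hypotension, dizziness, asthenia".

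**The concern.** By accepting a systolic fall of 30 mmHg alone, the (30) rule shows that the SAP does not require both pressures to fall. Yet no diastolic fall counts alone, whatever its size, and a systolic fall of 20–29 mmHg counts only with a diastolic fall of at least 10 mmHg. The SAP gives no reason for this.

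Safety and tolerability is the only secondary objective. Both arms receive olanzapine, so the table of subjects with orthostatic hypotension is the planned by-arm count of measured postural falls. If samidorphan changed mainly the diastolic response, or produced moderate systolic falls, that count could miss it. The supine and standing readings needed to see it are already collected.

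**Working it through.** **Logic.** The plan states no figure to reproduce, so the definitions are checked directly. Write S and D for the systolic and diastolic falls in mmHg on standing.

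- Current rules: (S ≥ 20 and D ≥ 10), or S ≥ 30.
- Either component: S ≥ 20 or D ≥ 10.

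| S / D | (20/10) | (30) | Either component |
|---|---|---|---|
| 20 / 10 | yes | no | yes |
| 30 / 9 | no | yes | yes |
| 29 / 9 | no | no | yes |
| 25 / 5 | no | no | yes |
| 19 / 40 | no | no | yes |
| 0 / 30 | no | no | yes |

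All integer pairs with S and D from −10 to 60 were enumerated. Of these, 1,730 meet a component but neither current rule, and they form exactly two regions:

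- (a) S of 20–29 with D < 10: 10 × 20 = 200 pairs.
- (b) D ≥ 10 with S < 20: 51 × 30 = 1,530 pairs.

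These are grid cells and say nothing about how many patients are affected.

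**Where else such a fall could be counted.** Table 5 is supine only. By-visit descriptive statistics summarise distributions and do not count falls. Listings show the readings without counting them. SAP 3.9.1 counts an event only if it is reported as an adverse event.

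**Illustrative size.** The documents give no means, SDs or correlation for postural change, so every input here is an assumption. Let X and Y be standing-minus-supine systolic and diastolic change, bivariate normal. The central case is X with mean −3 and SD 10, Y with mean +2 and SD 7, and correlation 0.6.

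- P(X ≤ −20) = Φ(−1.70) = 0.0446
- P(Y ≤ −10) = Φ(−1.714) = 0.0432
- P(both), the (20/10) rule = 0.0131
- P(X ≤ −30), the (30) rule = Φ(−2.70) = 0.0035, of which 0.0019 also has Y ≤ −10
- Current rules combined = 0.0131 + 0.0035 − 0.0019 = 0.0147
- Either component = 0.0446 + 0.0432 − 0.0131 = 0.0747
- Ratio, before rounding: 5.1

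The range takes all 32 combinations of systolic mean 0 or −6, systolic SD 10 or 12, diastolic mean +3 or −2, diastolic SD 7 or 8, and correlation 0.4 or 0.6. The ratio runs from 3.2 to 15.0. The comparator must be both current rules together; setting *either* against (20/10) alone would ignore the falls that (30) already captures.

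**Per subject.** The SAP counts subjects at any post-baseline visit. Protocol Table 3 has nine on-treatment post-baseline vital-sign visits (Visits 3, 4, 6, 8, 9, 11, 13, 15 and 17). Treating visits as independent overstates the cumulative rate, because repeat readings on one subject correlate. In the central case:

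- Current rules: 1 − (1 − 0.0147)⁹ ≈ 12%, about 25 of 200 per arm.
- Either component: 1 − (1 − 0.0747)⁹ ≈ 50%, about 100 of 200 per arm.

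**The case against.** The SAP sets two explicit, named thresholds in advance and applies them identically to both arms. The protocol defines no orthostatic hypotension, so nothing is contradicted. *And* and *or* both appear in the section, and Table 5 also combines its criteria with *and*, so a slip of the pen is not shown. All of this stands. A reader might infer that the definition is a mistake for *or*, or that it discards most of the qualifying falls. The documents support neither, because a fall qualifies only under a chosen definition and no *or* definition appears in either document.

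A reader might also infer that these falls are recorded nowhere. That goes too far: the readings are listed, they feed the descriptive summaries, and a reported event enters the adverse event tables. Adverse event reporting rests on investigator judgement, though, so it does not replace a measured count.

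Nor is it shown that the current rules leave too few events to compare arms. On the illustrative inputs about 12% of subjects could qualify over nine visits. Replacing (20/10) with an *or* rule could flag about half of subjects on the same inputs, many from ordinary variation, which might blur a difference between arms. That is a sound argument against redefining the category. It does not weigh against showing the components beside it.

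**Conclusion.** The gap follows from the definitions alone and needs no assumption: the two regions enter no orthostatic or PCS incidence table. Its size in subjects cannot be estimated from the documents. The 3- to 15-fold ratio is per measurement and rests wholly on assumed normal postural changes; the ratio per subject will differ.

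The consequence is limited to one descriptive safety table. Efficacy, Type I error and sample size are untouched, and the listed readings would allow other cuts later. The change is still worth making beforehand, because it concerns an effect that the protocol names as common with olanzapine and uses data already collected. It is a cheap improvement. Which definition of orthostatic hypotension is clinically right is not judged here.

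**What to change.** In SAP 3.9.3.1, keep (20/10) and (30) as defined. Add three rows to the same table, by treatment group, for subjects with each of the following on standing from supine at any post-baseline visit:

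- systolic fall of at least 20 mmHg;
- diastolic fall of at least 10 mmHg;
- either of these.

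The sponsor should also confirm that *and* is intended in (20/10) and add a sentence giving the reason.

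The cost is three descriptive rows and a short SAP edit, with no new measurements and nothing planned lost. The added rows will show higher and less specific rates in both arms, and should be read as components alongside the two existing categories.
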